### **8.3.9. Recording of Adverse Events and Serious Adverse Events**

When an AE/SAE occurs, it is the responsibility of the Investigator to review all documentation (e.g., hospital progress notes, laboratory reports, and diagnostics reports) related to the event.

The Investigator is responsible for ensuring all relevant information is recorded on the Adverse Event eCRF and SAE eCRF, as applicable.

The Investigator will attempt to establish a diagnosis of the event based on signs, symptoms, and/or other clinical information. Whenever possible, the diagnosis (not the individual signs/symptoms) will be documented as the AE/SAE. Avoid the use of vague, ambiguous, or colloquial expressions.

Refer to Section 8.3.1 and Section 8.3.6 for definitions of AEs and SAEs, respectively.

### **8.3.10. Pregnancy and Reporting**

A pregnancy is not considered to be an AE or SAE; however, any pregnancy occurring in a partner of a study subject during study participation or within 3 months of last dose of study drug

must be reported to the Sponsor using the Pregnancy Report Form not later than 24 hours after knowledge of the Pregnancy.

A pregnancy will be followed through to outcome. Once the outcome of the pregnancy is known, the Pregnancy Outcome Report Form is to be completed and reported to the Sponsor.

AEs and SAEs that occur during pregnancy will be assessed and processed according to the AE or SAE processes using the appropriate AE or SAE forms.

#### **8.4. Reporting of SAEs and DLTs**

The Investigator or designee will notify the Sponsor (see contact information on the cover page of this protocol) and the IRB, if necessary, immediately and not later than 24 hours after knowledge of the SAE or DLT. The Investigator will submit any updated event data to the Sponsor within 24 hours of it being available.

The following is a list of events that the Investigator must report to the Sponsor within 24 hours after learning of the event, regardless of relationship to study drug:

- SAEs (defined in Section 8.3.6).
- DLTs during the DLT assessment window (defined in Section 8.3.7).
- Pregnancies occurring in the partner of a study subject (see Section 8.3.10 for details on reporting requirements).

The investigative site personnel will be responsible for submitting the completed SAE /DLT and pregnancy reports to the Sponsor within 24 hours of discovery or notification of the events. The study site will be instructed to de-identify (i.e., blackout with permanent marker) associated medical records of confidential information prior to sending to the Sponsor.

The primary mechanism for reporting an SAE to the Sponsor will be an electronic SAE form that is completed and submitted to the Sponsor safety group.

Collection of SAEs during the course of the study are described in Section 8.3.9. Any SAE ongoing when the subject completes the study or discontinues from the study that are definitely, probably, or possibly related to study drug will be followed by the Investigator until the event has resolved, stabilized to  $\leq$  Grade 2, or returned to baseline status.

##### **8.4.1. Regulatory Reporting Requirements for SAEs**

Prompt notification by the Investigator to the Sponsor of an SAE is essential so that legal obligations and ethical responsibilities toward the safety of subjects and the safety of a study treatment under clinical investigation are met.

The Sponsor has a legal responsibility to notify both the local Regulatory Authority and other regulatory agencies about the safety of a study treatment under clinical investigation. The Sponsor will comply with country-specific regulatory requirements relating to safety reporting to the Regulatory Authority, IRBs/ECs, and Investigators.

Per 21 Code of Federal Regulations (CFR) 312.32, Investigator safety reports must be prepared for suspected unexpected serious adverse reactions, except those related to protocol-mandated

procedures according to local regulatory requirements and Sponsor policy and forwarded to Investigators as necessary.

An Investigator who receives an Investigator safety report describing an SAE or other specific safety information (e.g., summary or listing of SAEs) from the Sponsor will review and then file it along with the Investigator's Brochure and will notify the IRB/EC, if appropriate, according to local requirements.

## **8.5. Follow-up of AEs and SAEs**

After the initial AE/SAE report, the Investigator is required to proactively follow each subject at subsequent visits/contacts. The Investigator must continue to follow the subject until satisfactory resolution or stabilization, subsequent anti-cancer therapy is initiated, the subject is lost to follow-up, or the subject withdraws consent.

Procedures for follow-up of AEs and SAEs is as follows:

- The Investigator is obligated to perform or arrange for the conduct of supplemental measurements and/or evaluations as medically indicated or as requested by the Sponsor to elucidate the nature and/or causality of the AE or SAE as fully as possible. This may include additional laboratory tests or investigations, histopathological examinations, or consultation with other healthcare professionals.
- If a subject dies during participation in the study or during a recognized follow-up period, the Investigator will provide a copy to the Sponsor of any post-mortem findings, including but not limited to histopathology.
- New or updated information will be recorded in the originally completed eCRF.
- The Investigator will submit any updated SAE data to the Sponsor within 24 hours of receipt of the information.

## **9. STATISTICS**

### **9.1. Sample Size Determination**

#### **9.1.1. Phase 1 Dose Escalation**

In the Phase 1 portion of the study, 5 dose levels are planned to be evaluated in a dose escalation/de-escalation manner using a BOIN design to determine the MTD. The target DLT rate for the MTD is  $\phi = 0.3$  and the maximum sample size is approximately 27 across the 5 planned dose levels, with a maximum of 12 subjects treated per dose level.

The first 2 dose levels will use an accelerated titration design with a cohort size of 1 and will expand to a cohort size of 3 upon the first instance of a DLT, an existing Grade 2 condition that worsens to Grade 3, or a new Grade 2 AE. When this occurs then all higher dose levels will use a cohort size of 3 and follow the escalation/de-escalation/ elimination rule described in Section 9.5.1.

The dose levels to be tested will initially be 40, 80, 160, 300, and 600 mg orally once per day. Additional dose levels (e.g., intermediate levels or larger or smaller doses) or dosing schedules (e.g., twice daily) may be studied at the discretion of the SRC based on their review of safety data and any PK, pharmacodynamics, and efficacy data. If this does occur, then the number of dose levels of the BOIN design and total number of subjects included in the study will increase accordingly while using the same BOIN design for the escalation/de-escalation/elimination rules.

### **9.1.2. Phase 2 Dose Expansion**

In the Phase 2 portion of the study, up to 16 evaluable subjects will be randomized into each of 2 expansion dose cohorts and evaluated for efficacy using a Simon 2-stage minimax design to exclude a response rate of < 10%, where response is defined as having  $\geq 50\%$  reduction in PSA. The hypothesized response rate under treatment is  $\geq 40\%$  and will be evaluated using a one-sided type I error rate of 0.025 with 80% power. A total of 9 subjects per dose level will be randomly assigned in Stage 1. If at least 2 responses of  $\geq 50\%$  reduction in PSA are observed, the dose level will proceed to Stage 2. If at least 5 responses are observed in a total of 16 subjects per dose level, the null hypothesis will be rejected.

Randomized dose assignment will proceed when both cohorts are open for enrollment. If one of the dose levels is closed due to safety findings or lack of efficacy findings, or is paused until Stage 1 efficacy is observed, non-randomized assignments may proceed within the open dose level expansion cohort. This hypothesis will require a dose cohort total of 16 for a Phase 2 Dose Expansion study total of 32 subjects.

## **9.2. Populations for Analysis**

The DLT-evaluable Population is defined as all subjects in the Phase 1 Dose Escalation part of the study who receive ONCT-534 and either complete the 28-day DLT observation period or discontinue the study early due to a DLT. Subjects will be grouped by the dose received.

The Safety Population is defined as all subjects who receive at least one dose of ONCT-534. Subjects will be grouped by the ONCT-534 dose received at study entry.

The Efficacy-evaluable Population is defined as all subjects who receive ONCT-534 and complete at least one post-treatment disease assessment and do not discontinue due to clinical evidence of disease progression without documentation prior to obtaining post-treatment disease assessment. Subjects will be grouped by dose received.

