#### **4.1.1. Phase 1 Dose Escalation**

The Phase 1 portion of the study will use an adaptive Bayesian Optimal Interval (BOIN) Design (Liu et al., 2014; Yuan et al., 2016). The anticipated number of subjects in the Phase 1 portion is approximately 27 evaluable subjects, in 5 planned dose cohorts. The primary objectives are to assess the safety, tolerability, and DLT of ONCT-534 at escalating doses and to determine the MTD of ONCT-534 to inform the 2 dose levels or schedules to be tested in Phase 2. DLT will be assessed during the first 28 days of study treatment. DLT is defined in Section 8.3.7. The DLT assessment period will be from ONCT-534 administration on Day 0 through Day 28 and be based on DLT-evaluable subjects (Section 9.2).

The ONCT-534 dose levels to be tested will initially be 40, 80, 160, 300, and 600 mg orally once per day. Additional dose levels (e.g., intermediate levels, or larger or smaller doses) or dosing schedules (e.g., twice daily) may be studied at the discretion of the Safety Review Committee (SRC) based on their review of safety data and any PK, pharmacodynamics, and efficacy data.

The AR phenotype and AR levels of each subject's disease will be evaluated pre-treatment and on study based on analyses of circulating tumor DNA (ctDNA), circulating tumor cells, archival or fresh biopsy tissues, or on-study tumor biopsies (Section 8.1.10 and 8.1.11).

The SRC will review the safety, PK, pharmacodynamics, and preliminary efficacy data from each dose cohort in Phase 1 and will make the decision to escalate to the next dose level based upon their review of the data. The SRC will also propose the 2 dose levels or schedules to be tested in the Phase 2 expansion portion based upon available safety data, and any PK, pharmacodynamics, and efficacy data.

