**Table 2: Dose Modification of ONCT-534**

Toxicity	Treatment Modification
Grade 3 hematological toxicity	Hold treatment until recovery to Grade 1 or baseline; resume treatment at one level lower a . Transfusion and growth factors are allowed. Discontinue treatment if not resolved in 21 days.
Grade 4 or recurrent Grade 3 hematological toxicity	Hold treatment until recovery to Grade 1 or baseline; resume treatment at 2 dose levels lower a . Transfusion and growth factors are allowed. Discontinue treatment if not resolved in 21 days.
Grade 3 non-hematologic toxicity	Hold treatment until recovery to Grade 1 or baseline; resume treatment at one dose level lower a . Discontinue treatment if not resolved within 21 days.
Grade 4 non-hematologic toxicity	Permanently discontinue treatment.

a If the subject is receiving ONCT-534 at 40 mg/day, then reduce to 20 mg/day. If the subject is receiving ONCT-534 at 20 mg/day then discontinue treatment.

No dose modifications are required for the following:

- Grade 3 nausea/vomiting, anorexia, constipation, or diarrhea lasting for < 72 hours with optimal supportive care;
- Grade 3 fever lasting < 48 hours;
- Grade 3 blood urea nitrogen (BUN) or electrolyte abnormality that lasts up to 72 hours, is not considered clinically significant, and resolves spontaneously or responds to conventional medical interventions;
- Grade 3+ amylase or lipase that is not associated with symptoms or clinical manifestations of pancreatitis;
- Grade 3 fatigue, asthenia, or alopecia.

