### 8.3.7. Definition of Dose-Limiting Toxicity

DLT will be defined as any of the following attributed to ONCT-534 treatment occurring in the first 28 days of ONCT-534 treatment:

1. Any death not clearly related to the underlying disease or extraneous causes (e.g., accident or trauma).
2. Dose delays due to an AE lasting more than 14 days.
3. Non-hematologic toxicity:
  - a. Grade 3 or higher.
  - b. Hy’s law cases ([Appendix 1](#)).
  - c. AST or ALT  $> 8 \times$  ULN.
  - d. AST or ALT  $> 5 \times$  ULN lasting more than 14 days.
4. Hematologic toxicity
  - a. Grade 4 neutropenia or thrombocytopenia lasting more than 7 days.
  - b. Grade 3 or higher thrombocytopenia with clinically significant bleeding.
  - c. Neutropenic fever.

The definition of DLT will exclude:

- Grade 3 nausea/vomiting or diarrhea for less than 72 hours with adequate antiemetic and other supportive care.
- Grade 3 fatigue for less than 1 week.
- Grade 3 or higher BUN or electrolyte abnormality that lasts up to 72 hours, is not clinically complicated, and resolves spontaneously or responds to conventional medical interventions.
- Grade 3 or higher amylase or lipase that is not associated with symptoms or clinical manifestations of pancreatitis.

During the DLT evaluation period (Day 1 through Day 28 of study treatment) of the dose escalation cohorts, AEs identified as DLTs are required to be reported by the Investigator to the Sponsor immediately (no more than 24 hours after learning of the event), who will notify the SRC. Refer to Section 8.3.9 and Section 8.4 for recording and reporting procedures.

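### The DLT-evaluable definition sets no minimum exposure and does not say which dose counts after a reduction inside the 28-day window, so the DLT rate could be underestimated

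*Combined protocol and SAP*

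**What the plan says.** Section 9.2 counts as DLT-evaluable those Phase 1 subjects "who receive ONCT-534 and either complete the 28-day DLT observation period" or leave the study early because of a DLT. It adds: "Subjects will be grouped by the dose received". For the Safety Population, the same section specifies the dose at study entry; for the DLT population it does not. No section sets a minimum number of doses, a dose intensity or a compliance level for evaluability.

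Section 4.1.1 bases the DLT assessment on this population. The footnote to Figure 1 (Section 9.5.1) uses evaluable patients at the current dose as the denominator of the DLT rate. Section 7.2 uses the same definition to decide who may be replaced.

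Two other places determine who can be under-exposed and still DLT-free:

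- Section 8.3.7 limits DLTs as follows: "DLT will be defined as any of the following attributed to ONCT-534 treatment occurring in the first 28 days of ONCT-534 treatment". The list includes "Dose delays due to an AE lasting more than 14 days" and Grade 3 or higher non-hematologic toxicity, with stated exclusions. Hematologic DLTs are "Grade 4 neutropenia or thrombocytopenia lasting more than 7 days", Grade 3 or higher thrombocytopenia with clinically significant bleeding, and neutropenic fever.
- Table 2 says of Grade 3 hematologic toxicity: "Hold treatment until recovery to Grade 1 or baseline; resume treatment at one level lower". For Grade 4 or recurrent Grade 3 hematologic toxicity, the restart is two levels lower.

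**The concern.** BOIN treats each evaluable subject as one full 28-day trial of the dose. A subject who took the dose for only part of the window, and had no DLT, gives weaker evidence that the dose is tolerable but carries the same weight. If less exposure means less DLT risk, the observed rate falls below the full-exposure rate, and the rule escalates more often and de-escalates less often than it should. In a first-in-human study with at most 12 subjects per level, one such subject can decide the next step.

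The attribution gap adds to this. If a subject reduced within the window is counted at the higher level, that level is diluted. If he is counted at the lower level, that level gains a DLT-free subject whose toxicity arose at a higher dose.

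**Working it through.** **1. The plan's own figures.** Inputs from Section 9.5.1: target 0.3, boundaries 0.236 and 0.359, elimination if Pr(p > 0.3 | data) > 0.95 under a uniform prior. Assumed, because not stated: the usual BOIN defaults φ1 = 0.6 × 0.3 = 0.18 and φ2 = 1.4 × 0.3 = 0.42.

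- Escalation: ln(0.82/0.70) / ln[(0.30 × 0.82)/(0.18 × 0.70)] = 0.2365.
- De-escalation: ln(0.70/0.58) / ln[(0.42 × 0.70)/(0.30 × 0.58)] = 0.3585.

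Both agree with the stated values, and all 36 entries of Table 5 reproduce. The decision rule is sound; the issue is what enters it.

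**2. Which routes are open.** Setting Section 8.3.7 beside Table 2:

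| Situation in the window | Already a DLT? |
|---|---|
| Attributed AE delay of more than 14 days | Yes |
| Most Grade 3 or higher non-hematologic toxicity | Yes |
| AE hold of 14 days or less, no other DLT criterion met | No |
| Hematologic toxicity below the DLT threshold, restart one or two levels lower | No |
| Missed doses not caused by an AE, any length | No |

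**3. Effect of one subject on Table 5.** Removing one under-exposed DLT-free subject from the denominator:

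| Counted | Action | Without him | Action |
|---|---|---|---|
| 1/3 | stay | 1/2 | de-escalate |
| 1/5 | escalate | 1/4 | stay |
| 2/6 | stay | 2/5 | de-escalate |
| 2/9 | escalate | 2/8 | stay |
| 3/9 | stay | 3/8 | de-escalate |

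**4. A cohort of three.** Assume a constant daily hazard and no risk while off drug. A subject exposed for a fraction e of the window then has DLT risk 1 − (1 − p)^e. At p = 0.45:

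- Full exposure: P(0/3) = 0.55³ = 0.166.
- One subject at half exposure: risk 1 − 0.55^0.5 = 0.258, so P(0/3) = 0.55² × 0.742 = 0.224.

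**5. Range of dilution.** Let f be the share of under-exposed subjects and r their DLT risk relative to full exposure. Neither is in the documents. The observed rate is p × [1 − f(1 − r)]. With p = 0.40, Table 5 escalates on 0 or 1 DLT in 6:

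| f | r | Observed rate | P(escalate after 6) |
|---|---|---|---|
| 0 | – | 0.40 | 0.233 |
| 0.10 | 0.5 | 0.38 | 0.266 |
| 0.10 | 0 | 0.36 | 0.301 |
| 0.20 | 0.5 | 0.36 | 0.301 |
| 0.20 | 0 | 0.32 | 0.378 |

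**6. Whole-trial illustration.** Assumed true rates 0.05/0.12/0.30/0.45/0.60; 10,000 simulated trials per setting; cohorts of 3, N = 27, cap of 12 per level, isotonic MTD selection, accelerated titration omitted. The chance of selecting a dose above the true MTD is 21% with full exposure. It is 31% at f = 0.10, r = 0, and also at f = 0.20, r = 0.5. At f = 0.20, r = 0 it is 44%, and it falls to 23% if under-exposed DLT-free subjects are treated as non-evaluable without replacement.

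**The case against.** The strongest reply is that most of the off-drug route is already closed. Long attributed AE delays and most serious non-hematologic toxicity are DLTs, and the Grade 3 events excluded from the DLT definition also appear among the events for which Table 2 requires no dose change. The nonclinical target organs in Section 2.4.1 are kidney, liver, prostate and testis, so no hematologic signal is described. This stands: it narrows the concern to the three open routes and leaves their frequency unknown.

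Second, all dose moves are SRC decisions that BOIN only guides (Section 9.5.1), and under-exposure would be visible from PK samples, in-clinic dosing and returned tablets. During accelerated titration a new Grade 2 AE expands the cohort to 3, so a subject held for a new Grade 3 toxicity should not clear a level alone. That also stands, although a single subject with missed doses not caused by an AE still could. SRC discretion does not alter the counting rule, and no section requires the SRC to review exposure before counting a subject. The SRC Charter and the separate SAP may say more, but neither is in the document.

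Three stronger readings are tempting but not supported:

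- *The plan counts a reduced subject at his assigned dose.* Section 9.2 says dose received. The defect is that the rule is undefined after a mid-window change.
- *One dose followed by 28 days of observation is enough.* The literal wording of Section 9.2 does not exclude it, but Sections 4.1.1 and 8.3.7 describe the window as 28 days of treatment, and a subject who stops goes to an End of Treatment Visit. The point does not need this reading.
- *The DLT rate will be underestimated, by a large amount.* If all three cohort members had half exposure, P(0/3) at p = 0.45 would be 0.742³ = 0.408. That needs three under-exposed DLT-free subjects in one cohort, which the SRC would see. The documents support only that the rate could be underestimated.

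**Conclusion.** The point holds in limited form. As written, Section 9.2 lets a subject with materially reduced exposure count as a full DLT-free observation, and leaves open the level to which a reduced subject belongs. The direction of the bias, towards escalation, rests on DLT risk rising with exposure. Its size cannot be derived from the documents. The increase from 16.6% to 22.4% rests on a constant hazard, no risk off drug, a true rate of 45% and one half-exposed subject in three; time on a reduced dose would carry some risk and soften it. The Table 5 changes need no such assumption: one subject is enough to alter the prescribed action. The BOIN boundaries and Table 5 contain no error on this point. The change should be made because it is cheap and the definition feeds every escalation decision.

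**What to change.** Amend the DLT-evaluable definition in Section 9.2 as follows:

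1. A subject without a DLT is evaluable only if he took at least a prespecified share of planned doses at the assigned level during the window. The sponsor should justify the threshold; 75% is an example, not a figure from the documents.
2. A subject with a DLT is evaluable whatever his exposure.
3. The population is grouped by the dose level assigned at study entry. A subject reduced within the window is then not credited as DLT-free to either level unless he meets item 1.
4. Non-evaluable subjects follow Section 7.2.

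The hold, reduction and DLT rules need not change for this. Returned tablets (Section 6.2.1) and the exposure data to be summarized (Section 9.5.5) should supply what item 1 needs.

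The cost is an occasional replacement subject. Section 7.2 does not require replacement at cohort size 3, so without one a decision may rest on fewer subjects (1/3 stay becomes 1/2 de-escalate). The rule is also asymmetric, since it keeps under-exposed subjects with a DLT and drops those without. With p = 0.40, f = 0.20 and r = 0.5, the under-exposed contribute 0.20 × 0.20 = 0.04 in DLTs, and the expected rate is (0.80 × 0.40 + 0.04)/(0.80 + 0.04) = 0.36/0.84 = 0.43. That is slightly above the true 0.40, against 0.36 under the present definition, so the remaining error is on the cautious side. Holds in excluded subjects should still be reported to the SRC.

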## 7.2. Subject Replacement

The BOIN design does not require that subjects in the Phase 1 portion of the study who are not DLT evaluable (as defined in Section 9.2) be replaced unless the cohort size is one. Subjects who receive ONCT-534 and withdraw prior to Day 28 due to a DLT will not be replaced, and subjects who are not evaluable may be replaced at the discretion of the Sponsor and SRC.

Subjects in the Phase 2 portion of the study may be replaced, after discussing with the Sponsor, if they are not evaluable for efficacy (as defined in Section 9.2) for the purpose of estimating clinical activity of ONCT-534 and discontinued the study for reasons not related to study drug or disease progression.

Additional subjects may be enrolled beyond the planned sample size to provide sufficient data for analysis of safety, efficacy, PK and/or pharmacodynamics.

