## 9.5. Analysis of Endpoints

### 9.5.1. BOIN Design Implementation and Assessment of MTD

A BOIN design will be employed to find the MTD. The BOIN design is implemented in a simple way incorporating features of the traditional 3+3 design but is more flexible and possesses superior operating characteristics that are comparable to those of more complex model-based designs, such as the continual reassessment method (Zhou et al., 2018). Operating characteristics will be detailed in the SAP.

[figure not shown]
The target DLT rate for the MTD is  $\phi = 0.3$  and the maximum sample size is 27, using an accelerated titration design for the first 2 dose levels. DLTs are defined in Section 8.3.7, and those DLTs that occur within the first 28 days of treatment will be used for dose finding. As shown in

Figure 1, the BOIN design uses the following rule once it has moved from a cohort size of 1 to 3, optimized to minimize the probability of incorrect dose assignment, to guide dose escalation/de-escalation:

- If the observed DLT rate at the current dose is  $\leq 0.236$ , escalate the dose to the next higher dose level;

- If the observed DLT rate at the current dose is  $> 0.359$ , de-escalate the dose to the next lower dose level;
- If the above criteria are not met, remain at the current dose until a maximum of 12 subjects have been enrolled and treated at that dose level.

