**Figure 1: Flowchart for Trial Conduct Using the BOIN Design**

\* DLT rate =  $\frac{\text{Total number of patients who experienced DLT at the current dose}}{\text{Total number of evaluable patients treated at the current dose}}$

For the purpose of overdose control, doses  $j$  and higher levels will be eliminated from further consideration if  $\Pr(p_j > 0.3 \mid \text{data}) > 0.95$  and at least 3 evaluable subjects have been treated at dose level  $j$ , where  $p_j$  is the true DLT rate of dose level  $j$ ,  $j = 1, \dots, 5$ . This posterior probability is evaluated based on the beta-binomial model  $y_j \mid p_j \sim \text{binomial}(p_j)$  with  $p_j \sim \text{uniform}(0, 1)$ , where  $y_j$  is the number of subjects that experience DLT at dose level  $j$ . If the lowest dose is eliminated, the SRC will decide whether to stop the study or add a lower dose level. The

probability cutoff 0.95 is chosen to be consistent with the common practice that when the target DLT rate  $\phi \leq 1/6$ , a dose with 2/3 subjects experiencing DLT is eliminated.

The above dose escalation/de-escalation/elimination rule, which will be used to conduct the trial, is equivalently shown in

Table 5.

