**Table 5: Dose Escalation/De-escalation/Elimination Rule for the BOIN Design**

Actions*	The number of evaluable subjects at the current dose (cohort size n=3)											
	1	2	3	4	5	6	7	8	9	10	11	12
Escalate if # of DLT $\leq$	0	0	0	0	1	1	1	1	2	2	2	2
De-escalate if # of DLT $\geq$	1	1	2	2	2	3	3	3	4	4	4	5
Eliminate if # of DLT $\geq$	NA	NA	3	3	4	4	5	5	5	6	6	7

The steps to implement the BOIN design are described as follows:

1. All decisions to move from one dose level to another will be made by the SRC (Section 10.1.4), guided by the principles of the BOIN design.
2. Perform accelerated titration in dose cohorts 1 and 2 as follows. Treat the first subject in the cohort and escalate the dose in a one-subject-per-dose-level fashion until any of the following events is observed in the first 28 days of treatment: (i) a DLT, (ii) an existing Grade 2 condition that worsens to Grade 3; or (iii) a new Grade 2 AE. In such a case, the cohort size for the current and all subsequent cohorts will be increased to 3.
3. To assign a dose to the next cohort of subjects, the SRC will consider dose escalation/de-escalation rules presented in

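### The DLT-evaluable definition in section 9.2 omits a subject who has a DLT and then leaves before Day 28 for another reason, so the dose rule can be read three ways for that subject

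*Combined protocol and SAP*

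**What the plan says.** - **Section 9.2** gives two routes into the DLT-evaluable population. A treated Phase 1 subject must "either complete the 28-day DLT observation period or discontinue the study early due to a DLT".
- **Section 4.1.1** ties the DLT assessment to that population, with a window that runs "on Day 0 through Day 28 and be based on DLT-evaluable subjects (Section 9.2").
- **Section 8.3.7** defines a DLT without reference to whether or why the subject leaves, and starts the window a day later: "During the DLT evaluation period (Day 1 through Day 28 of study treatment").
- **Section 9.5.1** sets no condition on leaving: "those DLTs that occur within the first 28 days of treatment will be used for dose finding".
- **Figure 1** puts every patient with a DLT at the dose in the numerator of the DLT rate. The denominator is "Total number of evaluable patients treated at the current dose". Table 5 is also indexed by evaluable subjects.
- **Section 7.2** rules out replacement only when the withdrawal is because of a DLT. Otherwise "subjects who are not evaluable may be replaced at the discretion of the Sponsor and SRC". It also says that BOIN does not require subjects "who are not DLT evaluable (as defined in Section 9.2) be replaced unless the cohort size is one".
- **The steps after Table 5** leave the decision with the committee: "All decisions to move from one dose level to another will be made by the SRC".

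**The concern.** Take a subject with a DLT on Day 10 who withdraws consent on Day 20. He did not complete the window and did not leave because of the DLT, so under 9.2 he is not evaluable. Under 9.5.1 his DLT counts. Under Figure 1 he adds one to the numerator and nothing to the denominator. Under 7.2 a new subject may take his place.

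The observation is not missing. A DLT is a complete outcome on the day it occurs, and only a DLT-free subject needs the full 28 days. The definition treats this known outcome as unknown because of an unrelated later event. What is at stake is the dose action in a first-in-human trial, where three sections give three answers for the same data.

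**Working it through.** **1. Reproduce the plan's own rule.** The target DLT rate is 0.3 (9.1.1). With the usual BOIN defaults of 0.6 and 1.4 times the target, that is 0.18 and 0.42 (an assumption; the protocol does not state them):

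- escalation boundary = ln(0.82/0.70) / ln[(0.30 × 0.82)/(0.18 × 0.70)] = 0.2365
- de-escalation boundary = ln(0.70/0.58) / ln[(0.42 × 0.70)/(0.30 × 0.58)] = 0.3585

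These agree with the printed 0.236 and 0.359. Elimination uses a Beta(1 + y, 1 + n − y) posterior, Pr(p > 0.3) > 0.95 and n ≥ 3. All three rows of Table 5 match in all 12 columns, so Table 5 is sound. The question is which y and n go into it.

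**2. One affected subject, three readings.** Let y of n subjects at a dose have a DLT, one of whom leaves early for another reason.

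| Reading | Rate | n = 3, y = 1 | n = 3, y = 3 |
|---|---|---|---|
| Counted in full (9.5.1) | y/n | 1/3: stay | 3/3: eliminate |
| Dropped (9.2 with 4.1.1) | (y−1)/(n−1) | 0/2: escalate | 2/2: de-escalate |
| Figure 1 read literally | y/(n−1) | 1/2: de-escalate | 3/2: impossible |

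**3. All relevant cells.** Take n = 3, 6, 9 and 12, with y from 1 to the elimination count: 3 + 4 + 5 + 7 = 19 cells.

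- *Dropped under 9.2:* 6 of 19 change, all to a less cautious action. 1/3, 2/6 and 3/12 go from stay to escalate. 3/3, 4/6 and 5/9 go from eliminate to de-escalate.
- *Figure 1 literally:* 6 of 19 change, all to a more cautious action. 1/3, 2/6, 3/9 and 4/12 go from stay to de-escalate, 2/9 from escalate to stay, and 6/12 from de-escalate to eliminate. A seventh cell, 3/3, becomes 3/2.

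**4. How often.** The protocol gives no rate for such departures. Assume that each subject with a DLT has a chance w of leaving early for another reason, that nobody is replaced and that Table 5 is followed. With a first cohort of 3 and true DLT rate p, dropping under 9.2 gives

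P(escalate) = (1 − p + pw)³ − (pw)³.

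| p | w = 0 | w = 2% | w = 10% | Action changed (w = 2% to 10%) |
|---|---|---|---|---|
| 0.30 | 34.3% | 35.2% | 38.9% | 1.1% to 5.3% |
| 0.40 | 21.6% | 22.5% | 26.2% | 1.3% to 6.3% |

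For p = 0.30 and w = 10%: 0.73³ − 0.03³ = 0.389.

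If each dropped subject is replaced once and the replacement counts in full, P(escalate) = [(1 − p)(1 + pw)]³. At p = 0.30 this is 0.7042³ = 34.9% for w = 2% and 0.721³ = 37.5% for w = 10%. Replacement softens the shift but does not remove it.

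**5. Side check on Phase 2 Stage 1 membership.** The Simon rule (9 then 16 subjects, continue with at least 2 responses, reject with at least 5) has exact type I error 1.6% at a 10% response rate. Suppose 1, 2 or 3 of the 9 are Phase 1 subjects who reached the dose by escalation, each with a 19% response chance (assumed: two independent 10% chances, 1 − 0.9²). Rejection is then 2.0%, 2.4% or 2.9%, against the planned 2.5%.

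**The case against.** **The direction is not fixed.** A reader might infer that the plan discards these DLTs and so always leans towards escalation. The documents do not support that. The Figure 1 numerator is not limited to evaluable patients and 9.5.1 says the DLTs are used, so a literal reading of the formula errs towards caution. This stands: the defect is a conflict between sections, and it is less cautious only where 9.2 is followed.

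**Single-subject titration is largely protected.** Under 9.1.1 and the steps after Table 5, any observed DLT enlarges the cohort to 3, whether or not the subject is evaluable. This stands. It does not settle whether that first subject then counts at the dose, which is again 1/3 against 0/2.

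**The SRC sees the event.** DLTs reach the sponsor within 24 hours, the sponsor notifies the SRC, and the SRC makes each decision under a charter that is not in the supplied text. This limits the harm. It does not repair the rule that guides the SRC, and 9.4 promises the SAP only before database lock.

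**The case is rare and the frequencies are assumed.** This also stands. A subject who stops the drug but is followed to Day 28 arguably completes the observation period. In three of the six less cautious cells the next cohort still goes down, and only later re-use of the dose differs.

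**Safety grouping.** A reader might infer that 9.2 has no rule for dose changes in the safety tables. It has one: the dose at study entry.

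**Conclusion.** Wrong as written, in a narrow case. Section 9.2 leaves out a subject with an in-window DLT who leaves before Day 28 for an unrelated reason. This conflicts with 9.5.1 and with the Figure 1 numerator, and it leaves him replaceable under 7.2. The same data can mean stay, escalate or de-escalate.

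The conflict and the 6-of-19 cell count need no assumption beyond Table 5 itself. The 1.1% to 5.3% frequency at a 30% DLT rate rests on the assumed 2% to 10% departure rate and no replacement. SRC notification and the titration trigger keep the practical risk small, but this is a safety rule and should have one reading.

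Two neighbouring matters are lesser:

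- **AE tables.** Entry-dose grouping is defined, but events that start after the intra-patient escalation allowed by 4.1.3 appear under the entry dose. An added table would be a useful option. BOIN counts are unaffected.
- **Stage 1 membership.** This is a separate conflict: 9.1.2 has the 9 subjects randomly assigned, while 9.5.2 includes Phase 1 subjects at the same dose. A reader might infer that type I error is lost. On the assumed 19%, it stays under 2.5% with one or two escalated subjects and passes it with three.

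**What to change.** **Main change**

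- In 9.2, define DLT-evaluable as every treated Phase 1 subject with a DLT in the 28-day window, plus DLT-free subjects who complete the window.
- Use that one set in the numerator and denominator of Figure 1 and in Table 5.
- Align 4.1.1, 7.2, 8.3.7 and 9.5.1 with it, so that a subject with an in-window DLT is never treated as non-evaluable or replaceable.
- Reconcile the start of the window (Day 0 in 4.1.1, Day 1 in 8.3.7) to one definition.

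The cost is wording only. No subjects or visits are added, and Table 5 does not change.

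**Optional.** Keep the entry-dose safety tables and add AE tables by dose at onset, with subjects exposed and exposure time at each dose. Note beside them that escalators are selected for good tolerance. The cost is one more table set from dosing records.

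**Separate.** Reconcile 9.1.2 with 9.5.2 on whether Phase 1 subjects count among the 9 and, if so, whether those who reached the dose by escalation are included. Excluding them may mean a few more Phase 2 subjects.
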